# The Duke Primary Care Tailored to You (TTY) Blood Pressure Control Pilot Study

## Research Summary

### Research Abstract

Suboptimal blood pressure (BP) lowering therapy is a key reason for failing to reach hypertension control targets. Both clinical inertia and patient adherence contribute to suboptimal BP-lowering therapy. Impedance cardiography (ICG) is a simple, noninvasive method to assess a person's hemodynamic state and the pathophysiology contributing to high BP. Armed with such an understanding, a clinician can tailor medication selection to the individual patient. In this pilot study, we will test a protocol and procedures designed to investigate the clinical utility and feasibility of ICG-based hypertension therapy in the primary care setting. Twenty patients with uncontrolled hypertension (office BP $\geq$ 140/90 mm Hg) who are taking at least one BP-lowering medication will be enrolled in this study and followed for four-months. Participants will undergo ICG in the office setting during their clinic visit, and ICG assessment will be used to guide medication selection. Follow-ups with repeat BP measurement and ICG-guided medication titration will occur monthly until BP is controlled or four-months have passed. Outcomes (at four months) will be percent of patients who attain controlled BP and mean BP achieved as well as feasibility outcomes (enrollment and completion rates). This study is low-risk, carrying the same risks as standard care for patients with hypertension. Participants' BP will continue to be monitored in the standard manner in addition to ICG assessment.

*Primary study objectives:* To test procedures and gather preliminary data on the potential efficacy of incorporating impedance cardiography (ICG) into the assessment of patients with hypertension in the primary care setting to provide the clinician guidance on individualizing therapy to improve blood pressure (BP) control. Potential efficacy will be assessed as percentage of participants in whom BP control is attained.

*Secondary study objectives:* Collect preliminary data for informing a larger study.

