### Objectives & hypotheses to be tested

To assess feasibility and potential effectiveness of incorporating impedance cardiography (ICG) assessments into the care of patients with uncontrolled hypertension. As a pilot study, we will not be testing a hypothesis.

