### **Selection of Subjects**

We will recruit 20 patients (18 years or older) for this pilot feasibility study assessing ICG-guided hypertension management as an alternative to standard algorithm-based care (see Hypertension Medication Algorithm provided as an attachment) for improving BP control. Patients will be eligible if they have a documented diagnosis of hypertension (ICD 401.XX) and their most recent office systolic BP average measured using automated office BP (AOBP) is  $\geq 140$  mmHg systolic or  $\geq 90$  mmHg diastolic and they are currently prescribed at least one BP-lowering medication. All patients will already be under the care of a primary care clinician. AOBP is already the standard form of BP assessment in Duke Primary Care.

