### **Data Analysis**

As this is a pilot study for feasibility, our main outcomes will be enrollment and completion rates. Nonetheless, we will assess improvement in BP control (both percent at goal  $<140/90$  mmHg as well as average mmHg reduction in BP) at 4-months. For participants whose office BP is controlled prior to the 4-month visit, we will conduct a chart review to assess last clinic BP obtained, which will be entered into REDCap. Characteristics of participants will be tabulated by simple means and percentages. We will also tabulate number and categories of anti-hypertensive medications participants are prescribed.

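### Do the Research Abstract and the Data Analysis section disagree on which outcome leads, and does that matter in this pilot?

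*Protocol*

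**What the plan says.** The primary objectives in the Research Abstract have two parts, procedures and potential efficacy: "To test procedures and gather preliminary data on the potential efficacy of incorporating impedance cardiography (ICG". The only measure attached to them belongs to the second part: "Potential efficacy will be assessed as percentage of participants in whom BP control is attained". Earlier in the same section the outcomes are listed together without a ranking: "Outcomes (at four months) will be percent of patients who attain controlled BP and mean BP achieved as well as feasibility outcomes", with enrollment and completion rates then given in brackets as those feasibility outcomes.

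The section on objectives and hypotheses puts the two aims side by side: "To assess feasibility and potential effectiveness of incorporating impedance cardiography (ICG) assessments into the care of patients with uncontrolled hypertension". It adds that no hypothesis will be tested. Selection of Subjects describes recruitment "for this pilot feasibility study assessing ICG-guided hypertension management".

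The Data Analysis section is the only place that ranks the outcomes: "As this is a pilot study for feasibility, our main outcomes will be enrollment and completion rates". It continues with "Nonetheless, we will assess improvement in BP control", defined as the percentage below 140/90 mmHg "as well as average mmHg reduction in BP) at 4-months".

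**The concern.** Two things look wrong.

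First, a reader who goes from the primary objectives to the analysis finds a different lead outcome in each. The only measure printed beside the primary objectives is the BP control rate. The analysis section gives first place to enrollment and completion and treats BP control as an addition. If the study's lead outcome were truly undecided, the authors could choose after the fact whether to headline feasibility or BP control. That matters in an uncontrolled study that enrols on a high reading, because BP can fall on repeat measurement without any effect of impedance cardiography.

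Second, the continuous BP outcome is a mean level reached in the abstract and a mean reduction in the analysis section. These are different summaries, and a reduction also needs a baseline reading.

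**Working it through.** The protocol gives no alpha, power, effect size, precision target or success threshold, so there is no figure to reproduce. The check is a comparison of the texts.

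**Step 1: compare like with like.** Setting the efficacy measure in the abstract against the main outcomes in Data Analysis gives no overlap, but these are different kinds of item: one is the measure for part of an objective, the other is a ranking of the study's outcomes. The fair comparison is between the two outcome lists.

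| Outcome | Research Abstract | Data Analysis |
|---|---|---|
| Enrollment rate | listed | listed, main |
| Completion rate | listed | listed, main |
| Percentage with controlled BP | listed | listed, after the main outcomes |
| Continuous BP summary | mean level at four months | mean reduction at four months |

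Three of the four rows agree. The fourth differs only in the form of the summary.

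**Step 2: look for a rival ranking.** The abstract joins its outcomes without ordering them. The objectives section pairs feasibility with potential effectiveness. Selection of Subjects uses the feasibility label. Data Analysis then states an order, and that order fits the label. No passage says that the control rate is the main or primary outcome. That reading is an inference from its being the only measure printed beside the primary objectives. What is missing there is a measure for the part about testing procedures, and Data Analysis supplies it.

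**Step 3: level against reduction.** In participants with both readings,

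mean reduction = mean baseline BP − mean four-month BP.

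Given the baseline mean, each summary yields the other, and neither section excludes the other. Eligibility requires a most recent automated office BP average at or above 140 systolic or 90 diastolic, so every participant should have a reading before treatment is adjusted. Which reading serves as baseline, and how participants lacking one of the two are handled, are details commonly left to a statistical analysis plan. That plan may exist and is not at hand.

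**Step 4: what a different ranking would change.** The tabulated outcomes would be enrollment, completion, percentage at goal and the mean BP summary under either order. With no test, threshold or comparison arm, no error rate, power or pass/fail result depends on the order. The number of formal conclusions affected is 0.

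**The case for a change.** The best case for a change is that the Data Analysis wording does rank the outcomes, and it places the only measure tied to the primary objectives below two others that are attached by name to no labelled objective. The secondary objective, preliminary data for a larger study, does not name enrollment or completion either. The Background section pulls the other way, since it sets the goal of a greater proportion of patients reaching control beside a clinic-network control rate of 75.1%. A reader could therefore defend either headline. One agreed ranking would cost a few words, and it would keep the emphasis from depending on the results in a design where BP may improve by itself.

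Part of this stands. The objectives would read better if they named the feasibility measures, and both sections could name the level and the reduction. The warning about improvement without a treatment effect is also sound, but it comes from having no control group and enrolling on high readings, and reordering the outcomes would not remove it. The risk of a results-driven headline is small, because all the outcomes are named in advance and the analysis section already states which are the main ones.

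**Conclusion.** There is a minor misalignment of wording and no defect in the analysis. The abstract attaches a measure to the efficacy part of its primary objectives and none to the procedural part; Data Analysis names enrollment and completion as the main outcomes. The two fit together as an objective with two parts followed by a ranking of outcomes. Level and reduction are complementary descriptions that an analyst would report together.

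The effect is on the order of presentation only. No estimate, test or decision changes, so a change to the plan would bring no gain. This conclusion assumes that the study stays as described (one arm, 20 patients, descriptive results, no hypothesis and no progression threshold) and that all named outcomes are reported. If the control rate were later used as a formal criterion for going on to a larger study, the ranking would need to be stated explicitly.

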### Objectives & hypotheses to be tested

To assess feasibility and potential effectiveness of incorporating impedance cardiography (ICG) assessments into the care of patients with uncontrolled hypertension. As a pilot study, we will not be testing a hypothesis.

### Background & Significance

Control of high blood pressure (BP) is one of the most important strategies for prevention of stroke and cardiovascular diseases. In addition to the adoption of appropriate lifestyle modifications, from a clinical standpoint, achieving BP control requires several steps that culminate in choosing antihypertensive medication that is effective for the patient. In practice, BP-lowering medication is chosen empirically or based on clinical judgment taking into consideration clinical factors such as age, lifestyle and comorbidities. Ideally, however, BP-lowering medication should be matched to the patient's underlying

pathophysiology. Our central hypothesis is that hypertension control can be improved by addressing this gap.

In fact, a suboptimal medication regimen is the most common reason for uncontrolled BP. Some medications may simply not be effective for certain patients, and some medications can even cause a paradoxical BP increase. As opposed to the current strategy of choosing BP-lowering medications largely arbitrarily, measurement of hemodynamic parameters using impedance cardiography (ICG) may allow a better alignment of medication choice with a patient's underlying hypertensive pathophysiology. ICG provides information on vascular resistance and thoracic fluid status in addition to resting heart rate. A systematic review and meta-analysis of five studies suggested that ICG may be valuable as an adjunct to therapeutic decision-making in the treatment of hypertension.(Ferrario C, et al. 2010.) The review identified two randomized controlled trials (total 268 patients) of ICG-guided treatment with patients randomized to ICG-guided therapy about twice as likely to achieve BP control. However, both trials are dated, and baseline control rates were low (33% in one trial and 27% in another). Duke Primary Care, which uses the attached hypertension medication algorithm, currently has an overall 75.1% BP control rate. Our goal is to determine whether a tailored approach using ICG can facilitate an even greater proportion of our population attaining control of their BP, thereby reducing their risk for untoward cardiovascular events. This pilot study represents a first step in this line of research and quality improvement.

### **Design & Procedures**

The purpose of this pilot study is to test procedures and gather preliminary data on the potential effectiveness of incorporating impedance cardiography (ICG) into the assessment of patients with hypertension in the primary care setting to provide the clinician guidance on individualizing therapy to improve blood pressure (BP) control. ICG is not an experimental or investigational device; it is a low-cost, noninvasive technology that easily measures a person's hemodynamic phenotypic profile.

This pilot study will take place in the South Durham Duke Primary Care Clinic. The clinic serves approximately 15,700 patients, with an estimated hypertension diagnosis prevalence of 28.3%. As a pilot study, this will be a non-randomized, single-arm, prospective study. BP and ICG data will be recorded in a REDCap database. Data on BP-lowering medications will be collected by abstracting data from the EHR and entering it into the REDCap database.

The ICG system provides a printed report that indicates whether a person's hemodynamic state is predominantly one that is vasoconstricted, hyperdynamic, or mixed. The participating clinicians will have received teaching on the reports via a presentation delivered by one of the study investigators. Participating clinicians can refer to a separate table that provides a list of medication options suited to address each of these states based on their mechanism of action. The table was developed by MediSync for their MedEngine algorithm that is configured to align medication choices based on the hemodynamic findings from the ICG readings. This decision support tool was created so as to organize these medications based on their mechanism of action and is consistent with the evidence-based treatment of hypertension. In other words, the table is simply a way to organize BP-lowering medications matched to hemodynamic state according to their mechanism of action. The table lists appropriate standard of care medication options. The clinician can use the information to guide selection of the next BP-lowering medication. The ultimate decision on therapy rests with the patient's clinician. ICG data will not be put into the Duke SOC process. ICG data will not be incorporated in the DPC hypertension algorithm.

Participating clinicians will use clinical judgment, informed by ICG data and a table of standard of care BP medications for different hemodynamic states, to adjust medications.

For participants whose office BP is controlled prior to the 4-month visit, we will conduct a chart review to assess last clinic BP obtained, which will be entered into REDCap.

We will conduct anonymous surveys with both patients and providers who participated in the study to better understand acceptability and feasibility. These will be administered using REDCap and will include a short implied consent statement.

### **Selection of Subjects**

We will recruit 20 patients (18 years or older) for this pilot feasibility study assessing ICG-guided hypertension management as an alternative to standard algorithm-based care (see Hypertension Medication Algorithm provided as an attachment) for improving BP control. Patients will be eligible if they have a documented diagnosis of hypertension (ICD 401.XX) and their most recent office systolic BP average measured using automated office BP (AOBP) is  $\geq 140$  mmHg systolic or  $\geq 90$  mmHg diastolic and they are currently prescribed at least one BP-lowering medication. All patients will already be under the care of a primary care clinician. AOBP is already the standard form of BP assessment in Duke Primary Care.

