### **Subject Recruitment and Compensation**

Describe recruitment procedures, including who will introduce the study to potential subjects. Describe how you will ensure that subject selection is equitable and all relevant demographic groups have access to study participation (per 45 CFR 46.111(a) (3)). Include information about approximately how many DUHS subjects will be recruited. If subjects are to be compensated, provide specific prorated amounts to be provided for expenses such as travel and/or lost wages, and/or for inducement to participate.

Study staff will attend clinic days. Eligible patients of participating clinicians will be identified and informed about the study by the medical assistant. On study days, eligible patients of participating clinicians (who will have been trained on protocol) will be approached consecutively until the end of the clinic day or until target enrollment is complete. A study coordinator will work with the scheduled study clinician(s) and their medical assistant(s) to identify patients who may be eligible before the start of the clinic session. During the vital signs check-in procedures, the medical assistant will inform potentially eligible participants about the study if their check-in BP is  $\geq 140$  mmHg systolic or  $\geq 90$  mmHg diastolic. If an eligible patient is interested in participating, the medical assistant will introduce the patient to the study coordinator who will provide more information and obtain informed consent. Based on the number of patients with hypertension, it is estimated this pilot study will reach target enrollment in 5 or fewer study enrollment days. There is no compensation provided to participants. The ICG assessment will be provided free of charge.

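### Does the protocol leave open whether a patient qualifies on the enrolment-day blood pressure alone or must also have an elevated earlier chart value?

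*Protocol*

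**What the plan says.** The protocol's Selection of Subjects section gives the only blood pressure criterion: "their most recent office systolic BP average measured using automated office BP (AOBP") must be at least 140 mmHg systolic or at least 90 mmHg diastolic. It gives no visit and no time window. It adds that "AOBP is already the standard form of BP assessment in Duke Primary Care".

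The Subject Recruitment and Compensation section describes two steps. A study coordinator works with the clinicians and medical assistants "to identify patients who may be eligible before the start of the clinic session". Then, at vital signs, "the medical assistant will inform potentially eligible participants about the study if their check-in BP is" at or above the same two limits. Neither step uses the term AOBP.

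The Study Interventions section goes from hand-off to consent to the ICG assessment, with no other qualifying measurement in between. It describes the AOBP at the one-month visit as a repeat measurement.

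On outcomes, the Data Analysis section states that "our main outcomes will be enrollment and completion rates", and the Research Abstract states: "Potential efficacy will be assessed as percentage of participants in whom BP control is attained".

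**The concern.** The eligibility section and the recruitment section use different terms for the entry blood pressure. The first speaks of the most recent AOBP average. The second speaks of a check-in BP and of a candidate list made before any same-day reading exists. If that list were screened on chart BP, or if the check-in BP were something other than the AOBP average, a patient would in effect need two elevated values. Take a patient whose last chart AOBP was 134/82 and whose check-in BP is 146/84. That patient qualifies if the check-in reading is the qualifying AOBP, and does not qualify if the chart value must be elevated too.

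This could matter because the study has a single arm. Patients selected on a high reading tend to read lower later with no change in treatment, and this regression to the mean is stronger after one elevated visit than after two. The four-month control rate and mean reduction would contain different amounts of it under the two rules. The number of patients who must be seen to find 20 eligible ones would differ as well, which bears on the estimate of five or fewer enrolment days. Collecting data to inform a larger study is a stated objective, so the population should be identifiable.

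**Working it through.** **The text, side by side**

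| Question | What the protocol gives |
|---|---|
| Which value qualifies? | The most recent office AOBP average (Selection of Subjects) |
| How does the clinic measure BP? | By AOBP, as standard (Selection of Subjects) |
| What is measured on the day? | Check-in BP, at the same 140 and 90 limits (Subject Recruitment) |
| Is BP named as a criterion for the pre-session list? | No (Subject Recruitment) |
| Is there another qualifying BP before consent or ICG? | No (Study Interventions) |
| Is an earlier elevated BP required anywhere? | No |

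Once the check-in BP has been taken it is the most recent office value. For the chart value to count as well, the words would have to mean the visit before the present one. The pre-session list can be made from age, diagnosis, current prescription and participating clinician, all of which the chart holds. Patients are only potentially eligible until the day's BP is known. In the example, the most recent value is 146/84.

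**The size, if a two-visit rule did apply**

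The protocol gives no standard deviations and no figure to reproduce, so this is an illustration.

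Inputs:
- From the protocol: 15,700 clinic patients, hypertension prevalence 28.3%, control rate 75.1%, planned sample 20.
- Assumed: systolic BP only; the 75.1% read as the probability of a value below 140 at a single visit; between-patient SD 10, 12 or 15 mmHg; visit-to-visit SD 7, 9 or 11 mmHg; no therapy effect.

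Model: visit value = patient mean + visit deviation, both normal. The correlation between visits is r = SDb² / (SDb² + SDw²). With A, B and C denoting a value of at least 140 at the earlier, enrolment and later visit:
- eligible share on one visit = P(B) = 1 − 0.751 = 0.249
- eligible share on two visits = P(A and B)
- later value below 140 after one = 1 − P(B and C) / P(B)
- later value below 140 after two = 1 − P(A and B and C) / P(A and B)

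Results with SDb = 12:

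| SDw | P(A and B) | Below 140 later, one visit | Below 140 later, two visits | Gap |
|---|---|---|---|---|
| 7 | 0.158 | 0.366 | 0.237 | 0.130 |
| 9 | 0.140 | 0.438 | 0.303 | 0.136 |
| 11 | 0.126 | 0.496 | 0.363 | 0.133 |

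(The gaps come from unrounded values.) With SDb = 10 the gaps are 0.135, 0.134 and 0.124; with SDb = 15 they are 0.118, 0.131 and 0.136. Over all nine combinations the share below 140 later is 31% to 55% after one visit and 19% to 42% after two. A gap of 0.118 to 0.136 is 2.4 to 2.7 of 20 patients.

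Pool: 15,700 × 0.283 = 4,443 patients with hypertension. One visit: 4,443 × 0.249 = 1,106 eligible. Two visits: 4,443 × 0.113 to 4,443 × 0.173, about 502 to 769. Patients with hypertension seen per 20 eligible: 20 / 0.249 = 80, against 20 / 0.173 = 116 to 20 / 0.113 = 177.

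**Against the precision of the pilot**

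For 20 patients and a proportion of 0.5, the 95% half-width is 1.96 × √(0.5 × 0.5 / 20) = 0.219, about 22 percentage points.

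**The case for a change.** The strongest case for a change is that the match between check-in BP and AOBP average is an inference. The follow-up and endpoint readings are called AOBP averages; the check-in reading is not. The pre-session list has no stated criteria, so one coordinator could leave out patients with a normal last chart BP and another could keep them, and neither would breach the text. Eligibility belongs in the protocol rather than in an analysis plan, and one clause would settle it.

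Part of this stands. The terms do differ, and using the same one in both sections would be tidier. The direction of the effect is also sound: a separate simulation with other assumed values gave 24% to 53% below 140 after one elevated visit and 14% to 40% after two.

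The rest does not carry. A chart-based BP screen has to be read into the protocol, because no section mentions one. The calculation shows a smaller pool and a heavier screening load, not a different enrolment rate: if the rate is enrolled over approached or over eligible, the pool is already in the denominator. BP is recorded in REDCap, so the entry values can be reported and the population described. The size also depends on the assumptions. With a visit SD of 5 to 6 mmHg and a between-patient SD of 15, the gap falls to about 10 to 11 points. The model further ignores diastolic entry and the medication criterion, and it applies to one clinic a control rate given for Duke Primary Care overall.

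**Conclusion.** No change to the plan is needed. The text points to one reading: the enrolment-day check-in AOBP average qualifies the patient, and no earlier elevated value is required. This rests on the clinic's use of AOBP as standard, the identical thresholds, the reference to a repeat AOBP at one month, and the absence of any other qualifying measurement.

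The gap of 12 to 14 percentage points would arise only under a two-visit rule that the protocol does not state, and only with the assumed standard deviations. It lies within the sampling error of a 20-patient pilot that tests no hypothesis and has feasibility as its main outcome. Followed as written, the protocol gives a sound and describable result. What remains is a clerical difference between two names for the same reading.
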